Symptoms	Umbilical cord bleeding, cutaneous bleeding, gastrointestinal hemorrhage, intracranial bleeding, articular bleeding	Umbilical cord bleeding, cutaneous bleeding, gastrointestinal hemorrhage, intracranial bleeding, articular bleeding	No symptoms, or hemorrhage, thrombosis

Table 1:Types of Congenital Fibrinogen Deficiency

Source: Adapted from Acharya 2008

There are wide discrepancies in reported incidences of congenital deficiencies and the true incidence is largely unknown as some patients are asymptomatic. In countries/ populations where consanguineous marriages are frequent, the prevalence of recessive coagulation disorders is higher (Fried and Kaufman 1980, Lak et al. 1999, Khalid et al. 2008).

Effective management of congenital fibrinogen deficiency is necessary to prevent potentially life-threatening bleeding, to reduce increased loss of blood, transfusion requirements and the risk of surgery, and to improve pregnancy outcomes. Currently, conventional replacement therapy in fibrinogen deficiency given to counteract hemodynamic instability consists of transfusion of allogenic blood products such as *fresh frozen plasma* (FFP) and *cryoprecipitate*. The therapeutic target of these options is to achieve a fibrinogen activity concentration of at least 1 - 1.5 g/l (Peyvandi et al. 2006).

However, treatments with these preparations have certain limitations and moreover, expose the patients to multiple risks. As compared with fibrinogen concentrates, infusion of FFP or cryoprecipitate is limited by the lack of a virus inactivation/ removal process, leaving a potential risk of pathogen transmission (e.g., HBV, HCV, HIV). Moreover, both contain large amounts of proteins (fibronectin, von Willebrand factor, factor VIII, factor XIII, alpha macroglobulins, and anaphylatoxins), increasing the risk of allergic reactions (Silberstein et al. 1989, Sonntag et al. 1997). In addition, FFP and cryoprecipitate are insufficiently standardized in composition and must be thawed

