## 11.6 **Prohibited Medication or Treatment**

Blood donation or comparable blood loss within 60 days prior to infusion of BT524 for the pharmacokinetic assessment is not allowed.

Any concomitant medication *interacting relevantly with the coagulation system* such as

- fibrinogen concentrates other than BT524 (for prophylaxis or on-demand treatment)
- fresh frozen plasma
- cryoprecipitate
- low molecular weight heparin or unfractioned heparin
- factor Xa inhibitors (e.g., rivaroxaban, apixaban)
- factor IIa inhibitors (e.g., dabigatran)
- PY12 inhibitors (e.g., clopidogrel, prasugrel, ticagrelor) etc.
- and other blood or plasma derivatives

is prohibited 2 weeks prior to infusion of BT524 and within the study unless required by an emergency situation (major surgeries or major bleeding events that requires respective medication).

In case prohibited medication had to be administered for emergency situations details of the event, reason for intake, product administered, and the dosage must be recorded accurately in the eCRF at the corresponding visit. Moreover, in case fresh frozen plasma, cryoprecipitate or other blood or plasma derivatives had to be administered the virus safety measures on the product must be recorded.

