### 14.4.2 Specifications of Clinical Efficacy Parameters

### PART II

Efficacy of BT524 will be assessed as **secondary objectives**.

The following efficacy parameters will be assessed after each bleeding event:

- Overall **hemostatic response** to treatment with BT524 for each surgical procedure and each treated bleed as assessed by the investigator according to a 4 point scale: "none", "moderate", "good" or "excellent"
- Total loss of blood (e.g., intra- and postoperatively, re-bleedings), if applicable
- Units of other fibrinogen-containing products infused besides BT524 e.g., fresh frozen plasma or cryoprecipitate
- Units of transfusion products infused, e.g., allogenic or autologous blood (packed red blood cells, fresh whole blood), platelets
- Consumption of BT524 (doses per kilogram BW required pre-, intra- or postoperatively for effective treatment)

The following efficacy parameter will be assessed after wound healing is expected to be completed:

• Quality of wound healing, if applicable

With respect to the evaluation of efficacy, patients with multiple events are to be considered as *individual cases* in a primary analysis.

14.4.3 Methods for Assessing, Recording and Analyzing Pharmacokinetic Parameters *14.4.3.1 Determination of Fibrinogen Antigen* 

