### PART II

Units of other fibrinogen-containing products such as fresh frozen plasma, cryoprecipitate or alternative commercially available fibrinogen concentrates given to counteract hemodynamic instability will be documented and evaluated for each bleeding event (e.g., surgical intervention).

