### Part II

Efficacy will be evaluated based on ODP and/or ODT of bleeding events (i.e. surgical procedures, spontaneous or post- traumatic severe bleeding). Response will be assessed by the investigator by means of a 4 point scale ('none', 'moderate', 'good', and 'excellent'). Response rates will be presented with 95 % confidence intervals both considering each event as an individual case and considering events as repeated measurements within the same patient, if applicable (e.g. by General estimation equations with intra-subject correlation structure). Additionally, type of surgery, loss of blood intra- and postoperatively, quality of wound healing, units of other fibrinogen-containing products, and units of transfusion products will be considered. Moreover,
the consumption of BT524 required for effective treatment (bleeding events; pre-, intra-, post-operatively) will be calculated. Furthermore, MCF as a surrogate efficacy parameter will be evaluated also in part II of the study (non-confirmatory).

Details will be described in the statistical analysis plan.

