10.3 Secondary endpoint analyses of part II

Each of the below secondary efficacy parameters will be evaluated and descriptive statistics presented on event level from part II (ODP or ODT, each for minor events, major events and overall) for the overall population and each age group. More precisely, the following efficacy parameters after each event will be assessed:

Overall haemostatic response to treatment with BT524 for each surgical procedure and each treated bleed as assessed by the investigator according to a 4 point scale ("none", "moderate", "good" or "excellent") will be evaluated presenting response rates with 95 % confidence intervals for each scale and for the sum of excellent and good, classified as success. These event-based evaluations will be conducted according to two concepts:

- 1) descriptively (showing frequencies and percentages based on the event level FBE and PPBE analysis set) considering each event as an individual case and
- 2) by modelling considering events as repeated measurements within the same patient (based on FBE and PPBE), if applicable (e.g. by general estimation equations with intra-patient correlation structure). Provided sufficient numbers of ODT and ODP, minor /major events should be considered (e.g. analysis by type according to concept 1 above).

Overall haemostatic response will also be presented in pie chart and listed.

For each surgical procedure loss of blood (intra- and postoperatively, re-bleedings) will be listed considering each event as an individual case (based on the event level FBE and PPBE analyses sets).

In addition, loss of blood is to be rated by the investigator according to classifications (loss of blood is below/within/above the expected range for the procedure performed) for surgical bleeding events. These ratings will be evaluated presenting numbers and percentages of events considering each bleeding event as an individual case (cf. concept 1 above).

Descriptive analysis on event level (based on event based FBE and PPBE analyses sets) will be conducted for and also listed

- Units of other fibrinogen-containing products infused besides BT524 (e.g., fresh frozen plasma or cryoprecipitate) given to counteract hemodynamic instability at the day of BT524 administration or 1 day after.

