- Units of transfusion products infused, e.g., allogenic or autologous blood (packed red blood cells, fresh whole blood), platelets, given to counteract hemodynamic instability at the day of BT524 administration or 1 day after.

- Consumption of BT524 (dose per kilogram body weight, dose per infusion and total dose) required pre-, intra- or post-operatively for effective treatment of surgical bleeding events.
- Quality of wound healing assessed after wound healing is expected to be completed.

Furthermore, MCF as a surrogate efficacy parameter will be evaluated pre-dose and at 1 hour post-end of each IV infusion (including repetitive infusion for one bleeding event) by means of non-confirmatory t-test(s) pre/post comparison plus correlation between MCF and fibrinogen activity. Also MCF will be presented as a whisker box plot and also listed.

Descriptive summary statistics including changes from baseline for the fibrinogen activity will be provided for each age group. MCF and fibrinogen activity values from additional samplings (beside pre-dose and 1 hour post-dose) taken as required per investigator will be listed and not used in the analyses described above. These analyses will be conducted on event level, i.e. based on the event based FBE and PPBE analysis set. Otherwise, details correspond to those of part I analysis, except that the testing is considered as non- confirmatory.

With respect to the two evaluation concepts of efficacy, the concept when multiple events per patient are to be handled as individual cases is considered primary analysis within the framework of secondary analyses of part II.

Descriptive summary statistics and a listing for the fibrinogen antigen at screening will be provided for each age group on patient level (SAF, FAS, and PP analysis sets).

11 Safety

All assessments will be done for part I and part II separately.

APE-Set will be used to present overall numbers of AEs incl. NTEAEs. All safety analyses will be based on the SAF.

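### The part II counts of other fibrinogen and transfusion products carry a haemodynamic-instability condition that the endpoint definition lacks; read literally, product given to a stable patient drops out of the event-level tables.

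*SAP*

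**What the plan says.** The endpoint is described in two ways.

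**Without a condition on reason.** The protocol synopsis and Protocol 14.4.2 list the parameter as "Units of other fibrinogen-containing products infused besides BT524 e.g., fresh frozen plasma or cryoprecipitate", with a parallel item for transfusion products. Protocol 15.2.5 (Part II) says that "units of other fibrinogen-containing products, and units of transfusion products will be considered". Protocol section 9 and SAP section 3 speak of the requirement or need for these products, again without a reason.

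**With a condition on reason.** Protocol 14.4.5.2.3 says that units of other fibrinogen-containing products "given to counteract hemodynamic instability will be documented and evaluated for each bleeding event". Protocol 14.4.5.2.4 says the same of transfusion products. SAP 10.3 repeats the reason and adds a time limit. Other fibrinogen-containing products are those "given to counteract hemodynamic instability at the day of BT524 administration or 1 day after"; the second item is "Units of transfusion products infused, e.g., allogenic or autologous blood (packed red blood cells, fresh whole blood), platelets, given to counteract hemodynamic instability", followed by the same time limit.

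Protocol 11.6 prohibits other fibrinogen products and blood derivatives "unless required by an emergency situation (major surgeries or major bleeding events that requires respective medication". When they are used, "details of the event, reason for intake, product administered, and the dosage must be recorded accurately in the eCRF".

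**The concern.** A second fibrinogen source or a transfusion may be given because bleeding continues after BT524, in a patient whose circulation is stable. That use bears directly on whether BT524 was sufficient. If the instability wording works as a filter, the event-level summary omits it and keeps use in unstable patients.

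This matters because part II is open-label and uncontrolled, and its main clinical outcome is an investigator rating on four labels. Neither document gives criteria for those labels or a rule linking use of a second product to the rating. In SAP 10.3 the blood-loss analyses and BT524 consumption are confined to surgical events. For spontaneous and post-traumatic bleeds, the count of other products is therefore one of the few clinical checks on the rating. Any omission would run in favour of BT524.

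**Working it through.** The plan gives no figure for this endpoint, so there is nothing to reproduce. The check is a comparison of texts.

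| Place | Condition on reason | Condition on day |
|---|---|---|
| Protocol synopsis; 14.4.2; 15.2.5 | none | none |
| Protocol section 9; SAP section 3 | none | none |
| Protocol 14.4.5.2.3 and 14.4.5.2.4 | haemodynamic instability | none |
| SAP 10.3, both items | haemodynamic instability | day of BT524 or 1 day after |

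**Step 1: origin.** The reason wording in SAP 10.3 follows Protocol 14.4.5.2.3 and 14.4.5.2.4. The protocol is thus inconsistent with itself, and SAP 10.3 is inconsistent with SAP section 3. SAP 2.1 declares the SAP consistent with the protocol and does not mention the difference. Only the day limit is new in the SAP; it is a separate matter.

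**Step 2: can the affected case occur?** Yes. The exception in Protocol 11.6 turns on major surgery or major bleeding. It does not mention haemodynamic instability.

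**Step 3: apply each wording to one case.** Take a major bleed in which fresh frozen plasma is given on the day of BT524 because bleeding continues, with the patient stable.

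- Protocol 14.4.2: the units are counted.
- SAP 10.3 read literally: the day condition is met and the reason condition is not, so the event adds 0 units to the FBE and PPBE summaries (Tables 14.2.2.2.x; for transfusion products, 14.2.2.3.x).
- Listing 16.8.2 (SAF II): the title carries no reason restriction, so the use should appear.
- Concomitant medication (SAP section 9): the use contributes to a count of patients by ATC level 2, and is listed.

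**Step 4: do the other outputs replace the summary?** No. One is a listing, and the other counts patients, not units per event. The titles of the summary tables refer to all events, so a reader would take filtered counts as complete.

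**Step 5: can the filter be applied consistently?** Neither document defines haemodynamic instability or says how units given for another reason are handled. Two programmers could produce different tables.

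**The case against.** The strongest reply is that the phrase is description. Protocol section 6 uses the same words generically: "conventional replacement therapy in fibrinogen deficiency given to counteract hemodynamic instability consists of transfusion of allogenic blood products". Neither document says that only such units count. Elsewhere, when the SAP leaves data out, it says so explicitly, as with unscheduled MCF and fibrinogen activity samples in 10.3. In Protocol 14.4.5.2.3 the phrase governs documentation as well as evaluation. As a filter it would limit documentation to unstable patients, which conflicts with the recording duty in Protocol 11.6. The table titles show no reason filter either.

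Much of this stands. The descriptive reading is plausible, especially in the protocol. It is weaker in the SAP, where the phrase shares a clause with a day limit that is plainly a selection rule; a programmer could reasonably apply both. If the phrase is descriptive, deleting it loses nothing.

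It can also be said that the data are not lost, that non-emergency use of a prohibited product would be a protocol deviation tabulated under SAP 6.3, and that the investigator's rating may reflect the use. The first is right and limits the consequence. The second does not cover emergency use in a stable patient, which Protocol 11.6 permits. The third is possible, but no rule secures it.

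**Conclusion.** The inconsistency is real and should be corrected. On a literal reading of SAP 10.3, product given for continued bleeding in a stable patient is left out of the event-level summaries, and the need for other products is understated. This rests on the phrase being applied as a condition, which the documents permit but do not state.

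A reader might infer three stronger things that the documents do not support:

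- **That such use disappears from the report.** It does not: Listing 16.8.2 and the concomitant medication outputs should still show it.
- **That the SAP introduced the reason condition.** It took the wording from Protocol 14.4.5.2.3 and 14.4.5.2.4.
- **That the understatement can be given a size.** The documents state neither how often other products were expected nor what share of those patients would be unstable. Appendix 20.3 grades bleeds as minor or major and says nothing about haemodynamic state.

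The endpoint is secondary and descriptive. The one confirmatory test (MCF in part I), the sample size and the response rate are unaffected.

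**What to change.** In SAP 10.3 and in Protocol 14.4.5.2.3 and 14.4.5.2.4, delete the haemodynamic-instability phrase as a selection condition. State that all other fibrinogen-containing products and transfusion products infused for the event are counted, whatever the reason. Record the clarification in SAP 2.1. The day limit needs its own decision and is not settled by this change.

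Optionally, show the instability subset as a separate row, using the reason for intake that Protocol 11.6 requires, where it is recorded.

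The cost is a few words in each document, with no new data for the main count. Reported use of other products may look slightly less favourable. The documents do not show that the reason is stored as a coded field, so the optional row may require a simple classification of free text.

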10.2 Secondary endpoint analyses of part I

PD parameters defined for the secondary objective will be derived from concentration-time profiles using adapted methodology, non-compartmental analysis, compartment analysis, or population modelling, as required. Details related to the analysis of these PD parameters will be specified in separate PK analyses plans.

In the scope of this SAP, descriptive summary statistics, including changes from baseline for the fibrinogen activity (from part I), will be provided for each age group (based on SAF, FAS, PP, and PK population). Values from each age group will be evaluated by a one-sample t-test (pre-/post-comparison) and presented in a tabular format. Surrogate efficacy parameter MCF, assessed by fib-tem S, will be measured in part I pre-dose and at 1 and 8 hours post-end of each IV infusion in patients \geq 6 years. MCF will be measured pre-dose and at 1 hour post-end of infusion in children between 2 and $<$ 6 years and pre-dose and at the end of each infusion in children $<$ 2 years.

Descriptive statistics including change from baseline will be presented for each age group, i.e. $<$ 2 years, 2 to $<$ 6 years, \geq 6 to $<$ 12 years, 12 to $<$ 18 years, \geq 18 years (based on FAS, PP, and SAF population).

Values for the patients \geq 18 years will be evaluated by a one-sample t-test (pre-/post-comparison) and presented in a tabular format.

This analysis, done for both post-dosing time points, will be considered confirmatory for the 1 hour post-end of infusion assessment in patients \geq 18 years. Additionally, 95%-confidence levels will be calculated.

More precisely, the t-test will assess the mean difference $\mu_{1,0}$ between dependent measurements (1h post minus pre-treatment MCF difference; one sample) and test the null hypothesis $H_0: \mu_{1,0} < 0$ versus the alternative $H_1: \mu_{1,0} > 0$ at a two-tailed α -level of 0.05.

Correlation between MCF and fibrinogen activity pre-dose and at 1 and 8 hours post-end of each IV infusion will also be assessed in patients ≥ 6 years.

Note that (according to protocol section 14.4.5.2.5) consumption of BT524 (dose per kilogram body weight and total dose) during part I, calculated and presented in the framework of exposure and compliance (cf. section above), can also be assessed and interpreted as efficacy endpoint in respect to MCF.

Also the efficacy parameter MCF will be presented as a whisker box plot for FAS.

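### The Part II MCF t-test and MCF–activity correlation pool several events per patient with no allowance for within-patient dependence, so their p-values and intervals are not valid as written

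*SAP*

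**What the plan says.** SAP 10.3 evaluates Part II MCF before dosing and "at 1 hour post-end of each IV infusion (including repetitive infusion for one bleeding event) by means of non-confirmatory t-test(s) pre/post comparison". The same sentence also asks how MCF correlates with fibrinogen activity. On the unit of analysis the section adds: "These analyses will be conducted on event level, i.e. based on the event based FBE and PPBE analysis set". On method: "Otherwise, details correspond to those of part I analysis, except that the testing is considered as non- confirmatory". The Part I method (SAP 10.2) is a one-sample t-test on the post-minus-pre difference, with one difference per patient at each time point. It also provides for intervals: "Additionally, 95%-confidence levels will be calculated".

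Two concepts for handling several events per patient appear in SAP 10.3. The second is introduced under overall haemostatic response: "by modelling considering events as repeated measurements within the same patient (based on FBE and PPBE), if applicable". The section closes by ranking them: "the concept when multiple events per patient are to be handled as individual cases is considered primary analysis".

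Clustering is foreseen elsewhere. SAP 5.5 allows for multiple bleeding events per patient, and SAP 8.2 tabulates 1, 2, 3 and more than 3 infusions per event. SAP 8.2 also says how repeat infusions are combined for dosage (mean or sum). No such rule is given for MCF. The MCF outputs in Appendix 15.1 (14.2.2.6.1 to 14.2.2.6.14) are all on event level.

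**The concern.** In Part I each patient supplies one MCF difference, so a one-sample t-test is sound. Carried over to Part II, the same test treats several differences from one patient as separate cases. Changes within a patient may share recovery, endogenous level and dosing approach. If so, the pooled test overstates the information and lets a few frequently treated patients dominate. The same holds for a correlation pooled over events.

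The non-confirmatory label removes any claim on alpha, but it does not make an interval cover at its stated level. MCF is the surrogate efficacy parameter in both parts (protocol 14.4.1), so its interval and its correlation with activity will be read.

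**Working it through.** **Stated figure.** The only MCF calculation in the documents is for Part I (SAP 3.1): 15 patients, effect size 0.8, 80% power, two-sided 5%. Exact non-central t power for a one-sample test at d = 0.8 is 79.0% at n = 14 and 82.1% at n = 15, so 15 is the smallest n reaching 80%. (The 0.8 is a standardised effect, although printed in mm.) No sample size or precision is given for Part II MCF.

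**Inputs for Part II.** Planned patients: at least 36 (SAP 3, Table 1). Observations per patient (m) and ICC are not in the documents and are assumed here.

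**Formula.** Design effect DE = 1 + (m − 1) × ICC. Coverage of the naive nominal 95% interval ≈ 2Φ(1.96/√DE) − 1. A valid interval is wider by about √DE. Example with m = 3 and ICC 0.5: DE = 1 + 2 × 0.5 = 2.0; 1.96/√2.0 = 1.386; coverage 83.4%; width factor 1.41.

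For uneven counts, DE = 1 + ICC × (Σm²/Σm − 1). The illustration has 20 patients with 1 observation, 8 with 2, 4 with 4 and 4 with 10: Σm = 92, Σm² = 516, 516/92 = 5.61.

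| Assumed counts | ICC 0.1 | ICC 0.3 | ICC 0.5 | ICC 0.7 |
|---|---|---|---|---|
| 2 each | 93.8% | 91.4% | 89.0% | 86.7% |
| 3 each | 92.6% | 87.9% | 83.4% | 79.4% |
| 5 each | 90.2% | 81.4% | 74.2% | 68.5% |
| uneven (above) | 89.5% | 79.6% | 71.9% | 66.0% |

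Simulation with 36 patients and equal counts agrees to within about 1.5 percentage points; for three each it gave about 87%, 84% and 78% at ICC 0.3, 0.5 and 0.7. At ICC 0, or with one observation per patient, coverage is nominal. Using one mean change per patient, simulated type I error was 4.5% to 5.4% throughout.

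**Correlation.** With MCF and activity both clustered by patient but truly uncorrelated, a naive 5% test rejected in 7.4%, 11.1% and 16.1% of simulations (36 patients, three each, ICC 0.3, 0.5, 0.7). The range was 5.8% (two each, ICC 0.3) to 27.3% (five each, ICC 0.7).

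**The opposing effect.** Suppose each patient has two infusions and the second change is smaller by δ SD. The naive variance gains δ²/4, and the ratio of true to naive variance becomes DE/(1 + δ²/4).
- ICC 0.3 (DE 1.3): δ = 1 gives 1.3/1.25 = 1.04, coverage about 94%; δ = 2 gives 1.3/2 = 0.65, about 98%.
- ICC 0.5 (DE 1.5): δ = 1 gives 1.2, about 93%; δ = 2 gives 0.75, about 98%.

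A modest fall at repeat infusions offsets the clustering; a large one makes the interval too wide.

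**Effect on the finding of a rise.** At the Part I planning effect of 0.8, 108 observations give t = 0.8 × √108 = 8.3, or 8.3/√2.4 = 5.4 after correction at ICC 0.7. In the uneven case, 0.8 × √92 = 7.7, and 7.7/√4.23 = 3.7.

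**The case against.** **The row unit is not settled.** A reader might infer that the SAP enters every infusion as an independent row. The text does not say so. Measurement at each infusion sits beside analysis on event level, the plural t-tests could be run by infusion number, and the layout is in a table-shells document kept separately. This stands. It does not rescue the analysis, because several events per patient are still pooled under each of these readings.

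**Repeated measures are mentioned elsewhere.** Protocol 15.2.1 adds a repeated-measurements efficacy analysis for bleeding events and surgery. SAP 4.1.2.2 promises per-patient analysis of selected efficacy endpoints, and the end of SAP 10.3 refers to two concepts of efficacy evaluation. None of these clearly reaches MCF: protocol 15.2.1 names surrogate efficacy separately from efficacy, the SAP's selection is not specified, and no patient-level MCF output is listed.

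**The direction is not assured.** Repeat infusions may show smaller changes, which works against narrowness. Tailored dosing (protocol 11.1.1) and setting unmeasurable MCF to 1 mm (SAP 5.6) could also reduce between-patient variation in change. A negative ICC would reverse the direction: three observations at −0.1 give DE 0.8 and a type I error of 2.8%. All of this stands.

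**The population may be smaller than 36.** The Part I MCF t-test is for patients aged 18 and over, and the synopsis plans at least 18 of about 36 patients under 18. Whether that restriction carries over is unclear. The design effect depends on observations per patient, not on the number of patients, so the concern remains.

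**No decision rests on it.** The sole confirmatory test is Part I MCF at 1 hour. This stands and limits the weight of the point.

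**Conclusion.** The point holds in a limited form. As written, the Part II MCF analysis makes no allowance for within-patient dependence, so its p-values and intervals, and any inference on the correlation, are not valid.

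If within-patient correlation is positive and changes do not fall systematically over repeat infusions, p-values are too small and intervals too narrow. Across the tabulated scenarios coverage runs from about 94% (two observations each, ICC 0.1) down to about 66% (uneven counts, ICC 0.7). These are assumed ranges, since the documents supply neither an ICC nor event or infusion counts.

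Two stronger readings are not supported. One is that the intervals are certainly too narrow; the direction depends on quantities the documents do not give. The other is that the finding of a rise in MCF is in doubt; with an effect near the Part I planning value it would probably survive. That value belongs to the fixed Part I dose, so applying it to Part II is itself an assumption.

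**What to change.** Amend SAP 10.3 as follows:

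1. State the row unit for the Part II MCF analysis, and which pre-dose value a repeat infusion is compared with: its own, or the Day 0 value per event that SAP 5.5 defines as baseline.
2. Analyse the change at the first infusion of each event with a mixed model (random patient) or GEE clustered on patient, with a small-sample correction. One mean change per patient is a simple alternative; it weights patients equally rather than events.
3. Present second and later infusions separately.
4. Give the MCF–activity correlation an interval from a bootstrap that resamples patients.
5. Say whether the Part I restriction of the t-test to adults applies.

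No new data are needed. The cost is a short SAP amendment, slightly more programming and usually wider intervals. The event-level descriptive tables can stay as they are.
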